#### Size of sample

The sample size for the qualitative elements of the study will enable us to capture both a wide range of views and diverse perspectives to enable us to meet the objectives of the study.

This is a feasibility study so the sample size for the number of pharmacies has been pragmatically determined and to ensure sufficient data can be collected so the objectives of the research can be met.

For the e-survey, we compute that the estimated proportion of people who would say yes (i.e. are aware of the service) will be between 10% (precision 8.3% - 11.7%) and 30% (precision 27.4% to 32.6%) with a p-value for 95 confidence interval set at 0.05.

#### Sampling technique

For qualitative interviews, focus groups and workshops: purposive sampling will be used to ensure a wide range of lay and professional views to inform the intervention.

#### Phase 2: Sampling of pharmacies

A sampling framework will be used to recruit three pharmacies per the following category with a spread across different socio-economic areas (based on deprivation index from Office for National Statistics):

- Rural small pharmacy / rural large pharmacy
- Non-rural small pharmacy / Non-rural large pharmacy

Randomisation will then be conducted to give 2 pharmacies from each of the four categories as interventions (total of 8), and 1 pharmacy from each of the four categories as a control (total of 4).

#### RECRUITMENT

#### Phase 1:

#### 1. Scoping interviews

Scoping interviews will be held with relevant representatives of relevant referral organisations (for example – Women's Aid, Samaritans, Emergency Department, Mental Health Crisis Team, Adult Social Care Domestic Abuse Co-ordinator, the Police, Addaction (now known as "We are with you")). The CI already has existing contacts with many of these organisations, from the development work. The CI will e-mail representatives from each organisation, supply information about the study and/or offer an introductory call. If the representative expresses an interest in participating the CI will forward the participant information sheet and consent form, and will make arrangements for an interview at a convenient time for the participant.

#### 2. Lay focus groups

Members of the public will be invited to participate from relevant patient forums, relevant charities, survivor support groups, the local Recovery College etc. via distribution of a flyer (and social media post). This will be done through a contact at those organisations.

#### 3. Co-development workshops

Lay people: Members of the public will be invited from relevant patient forums, relevant charities, survivor support groups, the local Recovery College etc. via distribution of a flyer (and social media post) through a contact at those organisations. Expressions of interest will be followed up with a participation information sheet, consent form and a phone call from the researcher. In addition, participants from the lay focus groups will be invited to continue with the study and participate in a co-development workshop.

Pharmacy staff representatives: Pharmacy staff will be identified via the Lincolnshire Training Hub. To ensure that different staff are invited in the co-production workshops and intervention delivery, recruitment to both research activities will be conducted in parallel. This will ensure there is no contamination in the delivery of the intervention.

#### Phase 2:

#### 1. Delivery of the service in pharmacies

Pharmacies will be identified and invited through the Local Pharmaceutical Committee (LPC) using purposive sampling. These will be randomised to intervention / control.

Pharmacy staff will be recruited from each intervention pharmacy. The Pharmacy Staff will consent to being trained and delivering the intervention, attending a feedback focus group and participating in the summary workshop, in one consent process at the beginning.

Service users will be recruited from intervention pharmacies, at the point where they make access to the service (i.e. clients make their own approach to use the service, and recruitment is part of accessing the service). There are two categories of data collected in the intervention consultation, Part A data consists of the essential information required to deliver the service to the client. Part B consists of supplementary data for the purposes of the research study. In emergency cases where time is pressured, or where the client does not consent to Part B data, the service will still be offered to the client without collecting Part B data. Pharmacy staff have a normal duty of care to offer care to customers and patients approaching them for help. This study will not interrupt that normal duty of care.

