# PRIMARY OBJECTIVE

How feasible and acceptable is a co-produced community pharmacy response intervention for identifying and referring people in danger from suicidal ideation or domestic abuse?

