### **OUTCOME MEASURES/ENDPOINTS**

#### PRIMARY OUTCOME MEASURE/ENDPOINT

The primary outcome measure for this study will be the number of community pharmacy consultations for people enquiring about or seeking support for domestic violence or suicidal ideation, categorised per issue and level of severity.

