# Phase 2: Feasibility cluster Randomised Control Trial

Pharmacy staff (to be trained, deliver the intervention, and participate in focus group and feasibility workshop)

- (a) Aged ≥18 years
- (b) Employed by a community pharmacy that is in the study

Clients (service users, (recipients of the intervention)

- (a) Aged  $\geq$ 18 years
- (b) Asking about or requiring support about domestic abuse / suicidal ideation

Pharmacy customers (for interviews)

(a) Aged  $\geq$ 18 years

(b) Familiar with the intervention pharmacy

General public (for community e-survey)

(a) Aged  $\geq$ 18 years

(b) Resident in Lincolnshire

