# a. Usage and referral data

The rationale for this intervention is to lower access barriers. The primary area of interest is therefore the number of consultations, severity of danger and number of referrals made as a consequence of the consultation. Other measures we will explore include the reasons why the client chose the service, whether the client was considering or had accessed other services in the last 3 months,

The member of staff conducting the consultation will record the date, time, length of consultation, job role of staff member and the category of issue. Following triage, the informed consent will be received from the client. Data to be collected will include asking the client what services he/she has accessed in the last 3 months, and whether he/she has accessed this service previously. The client will then be asked some simple questions about reasons for choosing this service based on the four access barriers (capacity, psychological burden, timing and level of severity), for example: no appointment needed, convenient location, everyday environment, identified with the name and logo, convenient timing, familiar environment, familiar staff, whether their visit was opportunistic or planned, and basic demographic data.

Brief acceptability data will also be collected along with basic demographic details plus an indication of whether (for a future trial) completing a questionnaire and having a follow-up contact would be acceptable or not.

Staff will be trained to respond ethically in all cases of acute and severe distress by prioritising the safety and wellbeing of the client over the need to consent and collect data for the study. In some cases, this may mean that it may not be appropriate under very distressing circumstances to collect all of the client's study data.

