#### b. Business data

Business data will be collected in order to evaluate whether taking on the service detracts or enhances normal pharmacy activity. Data will include prescription and service items. These data will be collected at the beginning of the study retrospectively for the 6 months prior, and during the 6 months of the implementation. All costs of the intervention will also be recorded.

In the control (comparison) pharmacies, the same business data will be collected in addition to the number of queries or interventions made for domestic abuse, and for suicidal ideation, and whether any of these were through an alternative scheme (for example "Ask for ANI"). We are including control pharmacies as this will provide useful data for a future trial and because we anticipate that the baseline levels of requests for assistance with DA will increase with public awareness of "Ask for ANI".

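### The main outcome counts a differently worded event in each arm: contacts started by staff can enter the control count but not the intervention count, and no listed field would show it.

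*Protocol*

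**What the plan says.** The protocol describes the event behind its main outcome in several places.

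- **Primary objective:** an intervention "for identifying and referring people in danger from suicidal ideation or domestic abuse".
- **Inclusion criteria, Phase 2, clients:** adults "Asking about or requiring support about domestic abuse / suicidal ideation".
- **Recruitment, Phase 2, 1. Delivery of the service in pharmacies:** "clients make their own approach to use the service, and recruitment is part of accessing the service".
- **Primary outcome measure/endpoint, repeated under Data analysis, Quantitative data:** the "number of community pharmacy consultations for people enquiring about or seeking support for domestic violence or suicidal ideation", split by issue and severity.
- **Data collection, b. Business data (control pharmacies):** "the number of queries or interventions made for domestic abuse, and for suicidal ideation", with a note of whether an alternative scheme was involved.
- **Schedule of procedures (control pharmacies):** enquiries and referrals.
- **Appendix 1, criterion 27 (control pharmacies):** queries, plus any requests under the existing schemes.

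For each consultation in the intervention arm, staff "record the date, time, length of consultation, job role of staff member and the category of issue". Other items cover services used in the last three months, earlier use of this service, reasons for choosing it, whether the visit was opportunistic or planned, and demographics. Appendix 1 criterion 18 adds who accompanied the client.

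Under Quantitative data, the arms are compared descriptively and by linear regression, with 95% confidence intervals. The results are to inform the sample size of a future trial.

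**The concern.** A difference between arms can be interpreted only if both arms count the same thing. Here the intervention-arm definition is tied to the client's own initiative: the person enquires, seeks or approaches. The control-arm wording in the Business data section is not, because an intervention made by staff need not follow a request. Eligibility and the objective add to the ambiguity, since requiring support and being identified do not by themselves presuppose asking.

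What is at stake is the between-arm difference. It is one of the few quantitative results this study passes to a definitive trial, and Appendix 1 criterion 35 asks for feasible differences in the primary outcome. A difference distorted by definition would carry over into that planning. With 8 intervention and 4 control pharmacies, there is little other information against which to detect the distortion.

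**Working it through.** The protocol states no figure to reproduce, so the first step is to set the wordings side by side. The question is whether a contact opened by a member of staff, with a person who did not ask, falls within each wording.

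| Place in protocol | Arm | Staff-started contact included? |
|---|---|---|
| Primary outcome; Quantitative data | stated for the study | No, on the wording |
| Recruitment, Phase 2 | intervention | No, on the wording |
| Inclusion criteria, clients | intervention | Possibly (requiring support) |
| Business data | control | Yes, as an intervention made |
| Schedule of procedures | control | Possibly, if it led to a referral |
| Appendix 1, criterion 27 | control | No, if only queries are logged |

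Next, could the data separate the two kinds of contact afterwards? None of the listed items records who raised the issue. The nearest is opportunistic or planned access (criterion 23). That describes the client's visit: a planned visit for another purpose can still become a conversation that staff open. The protocol collects all client data in the consultation and rules out later contact with clients (ethical section on collecting data from service users), so the information could not be obtained from them later. The control count is also not split by who started the contact.

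The possible size follows from simple algebra. Let the mean number of contacts per pharmacy be λ_I (intervention) and λ_C (control), with staff-started shares s_I and s_C. Suppose intervention pharmacies count client-started contacts only and control pharmacies count all contacts.

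- Like-for-like ratio of client-started contacts: R = λ_I(1 − s_I) / [λ_C(1 − s_C)].
- Observed ratio: λ_I(1 − s_I) / λ_C = R × (1 − s_C).
- Shift in the difference in means: [λ_I(1 − s_I) − λ_C] − [λ_I(1 − s_I) − λ_C(1 − s_C)] = −s_C × λ_C.

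The protocol gives neither s_C nor λ_C. The values below are assumptions, with λ_C = 10 contacts in six months for illustration.

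| Assumed s_C | Ratio multiplied by | Shift in difference at λ_C = 10 |
|---|---|---|
| 0% (or control logs queries only) | 1.00 | 0 |
| 10% | 0.90 | −1 |
| 25% | 0.75 | −2.5 |
| 40% | 0.60 | −4 |

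Under this pairing of definitions the shift goes one way: the intervention looks less used, relative to control, than it is.

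**The case against.** The strongest reply is that the service is client-led by design. It is a response service with a code word or symbol for discreet access. It is promoted to the public, and staff are trained to respond to requests for help. Eligibility applies to people already using the service, so requiring support may simply mean needing help rather than information. This stands as a reading of the intervention arm, and it is a good reason to keep client-started contacts as the main count. It does not explain why the control wording is broader.

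Two stronger readings are tempting, and the protocol does not support either.

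- A reader might infer that the identifying part of the primary objective goes unanswered. The triage questions assign each client a type and level of risk, and the outcome is categorised that way. That is a fair sense of identifying. The remark about a simple opening question prompting change comes from the team's earlier focus-group study and does not show that staff will open contacts here.
- A reader might infer that some intervention staff will follow the eligibility wording and others the recruitment wording, adding noise between pharmacies. Staff are to work from one Pharmacy Operating Manual, with training, mock consultations and monthly fidelity visits. Nothing suggests that they would apply separate protocol sections.

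It is also fair to say that data collection tools were still to be refined in Phase 1, so the field list is not closed, and that no sentence expressly excludes staff-started contacts. Both points soften the concern. They do not remove the conflict in wording, which lies in the protocol's own outcome, recruitment and control-data sections.

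**Conclusion.** The point holds as an inconsistency in the definition of the counted event, across sections and between arms. Staff-started contacts can be counted in control pharmacies and left out in intervention pharmacies, and the listed data could not reveal or correct this. The between-arm difference may therefore partly reflect definition.

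The size is unknown. It depends on the staff-started share in control pharmacies, which the protocol does not give, and on which of the three control wordings is used in practice. The effect is nil if only queries are logged. The ratios of 0.90 to 0.60 rest on assumed shares of 10% to 40% and show scale only. The conclusion does not extend to variation between pharmacies within an arm, or to whether the primary objective can be answered.

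**What to change.** - Reconcile the primary objective, primary outcome, Quantitative data, client inclusion criteria, Phase 2 recruitment, Business data, schedule of procedures and Appendix 1 criterion 27 to one counted event, worded identically for both arms.
- Add one field, started by client / started by staff, to the intervention record and the control log.
- Keep client-started contacts as the main like-for-like comparison, which respects the client-led design. Report staff-started contacts separately in each arm.

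The cost is wording changes in those sections, one tick box per consultation in the intervention arm, and a split tally in the control arm. The downside is slightly more recording by staff. Nothing about the care offered to clients changes.

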#### 2. Focus Groups with pharmacy staff who delivered the intervention

These participants will be those who have consented to be trained and deliver the intervention. If participants are unable to attend a focus group, we will offer a one to one interview instead. We will ensure that we collect feedback from all 24 participants in a manner that is convenient to them.

#### 3. Customer interviews

Customers will be identified by pharmacy staff and who are regular 'general customers' rather than specific clients who have asked to use the service.

#### 4. Public survey

Participants for the e-survey will be identified through distribution by local community venues, such as supermarkets, post offices, sports venues, faith venues etc.

#### 5. Summary workshop

Participants at the summary workshop will consist of the Pharmacy Staff who delivered the intervention, the PPIE Panel and the Study Management Group (research team).

In all of the above cases, the researcher will inform the potential participant of all aspects pertaining to participation in the study. It will be explained to the potential participant that entry into the trial is entirely

voluntary and that their treatment and care will not be affected by their decision. It will also be explained that they can withdraw at any time but attempts will be made to avoid this occurrence. In the event of their withdrawal it will be explained that their data collected so far may not be erased in accordance with the University's Research Privacy Notice and information given in the Participant Information Sheet and we will seek consent to use the data in the final analyses where appropriate.

#### **Participant Payment**

Should any participant be required to travel to a venue for the study, reasonable reimbursement of travel expenses will be offered.

#### Phase 1:

- Lay focus groups: £40 Amazon gift voucher per participant as a token of appreciation.
- Co-production workshops: £75 appreciation payment per participant or Amazon voucher (participants can choose a direct payment or a voucher).

#### Phase 2:

- Pharmacies: Intervention pharmacies will receive an expenses payment of £1500, and control pharmacies a payment of £500.
- Customer interviews: Customers will receive a £15 Amazon gift voucher as a token of appreciation of their participation.
- Public e-survey: Prize draw of 1 x £100, 1 x £60 and 2 x £40 Amazon vouchers (appreciation payments)
- Workshop: Pharmacy staff participants will receive a £75 fee for participating as a token of appreciation (or a voucher if preferred), as this will be an additional event after the 6 months implementation, for which the pharmacy received a fee.
- Refreshments will be provided at training, focus groups and workshops.

#### CONSENT

All participants shall provide written consent. The Informed Consent Form (ICF) will be signed and dated by the participant before they enter the study. The consent process will involve a discussion between the potential participant the researcher to ensure that the individual is fully informed about the research, including the nature and objectives of the study and possible risks associated with their participation. Opportunity will be given for potential participants to ask questions. Mental capacity will be assumed unless proven otherwise.

For the Phase 2: e-survey, return of the questionnaire will imply consent.

In some instances, electronic consent may be appropriate (i.e. if there are future COVID-19 restrictions and face-to-face interactions are not allowed). The University of Lincoln e-Consent guidance will be followed which is produced in accordance with the joint HRA and MHRA statement on seeking consent by electronic methods.

The recruiting Investigator will explain the details of the study and provide a Participant Information Sheet (and any other study related literature), ensuring that the participant has sufficient time to consider participating or not. Opportunity will be given to the participant to ask any questions they may have concerning study participation. For the e-survey, information about the study will be provided.

The process for obtaining participant informed consent will be in accordance with the REC guidance, and Good Clinical Practice (GCP), and any other regulatory requirements that might be introduced. The researcher and the participant shall both sign and date the Informed Consent Form before the person can participate in the study.

One copy of the ICF will be kept by the participant, one will be kept by the Investigator. Should there be any subsequent amendment to the final protocol, which might affect a participant's participation in the trial, continuing consent will be obtained using an amended Consent form which will be signed by the participant.

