To ensure we collect data about service use and acceptability, we will seek to collect basic demographic data and brief views on service acceptability when service-users access the service. The pharmacy staff will explain this is a trial service and invite the individual to offer their views. The data will be collected during the consultation. The consultation will take place in a private consultation area to ensure privacy. Potential participants will be informed that all data collected for the research is anonymised.

Consent (for Part A and Part B as appropriate) will be obtained at the time of contact. Clients will be provided with a Participant Information Sheet and Participant Consent Form. Because of the nature of the service, prior consent is not possible and there is a limited time frame for the initiation of the intervention being tested. We recognise that the usual 24 hour notice period will therefore not apply.

The pharmacy staff will go through the participant information sheet with the service user. They will be invited to take this away if they choose. Information sheets will be made available in the additional languages of Polish, Lithuanian, Hindi and Urdu.

It will be explained that offering study information is entirely voluntary and declining to provide this additional information will not affect the care they receive in any way. Pharmacy staff will check for understanding and provide the opportunity for potential participants to ask questions and withdraw their consent at any time.

In terms of data collection, all of the client data is collected in the consultation. We did not feel that contacting participants after the service to collect follow up data would be appropriate (risk of breach of confidentiality / potential to raise suspicions with abusive partners).

The study data collected will not be extensive. It will comprise of simple demographic data, brief views about acceptability, satisfaction and health status. We already have extensive PPIE input in the design of these procedures. We will further test these as part of Phase 1 (co-development) of the study where we anticipate there will be further refinement of the triage process, referral and data collection tools.

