# DATA PROTECTION AND PATIENT CONFIDENTIALITY

All study staff and investigators will comply with the principles of the Data Protection Act (2018) in protecting the rights of study participants with regards to the collection, storage, processing and disclosure of personal information and will uphold the Act's/Regulations core principles.

Each participant will be assigned a study identity number, for use on CRFs other trial documents and the electronic database.

Personal data, research data and the linking code will be stored in separate locations. When stored electronically, this will include using encrypted digital files within password protected folders and storage media. Personal information shall be stored separately to research data and will be kept secure, and maintained.

Personal data will be stored for 12 months following the end of the study, so that the Chief Investigator may provide participants with a summary of the research (should they wish to receive a copy).

Data generated as a result of this study will be available for inspection on request by the participating physicians, the University of Lincoln representatives, the REC, local R&D Departments and the regulatory authorities.

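### The consent section has every consenting service user keep a signed consent form, although the protocol gives up client follow-up data for fear of alerting abusive partners

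*Protocol*

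**What the plan says.** The Consent section opens with a rule of general scope: "All participants shall provide written consent". It ends with the copy rule: "One copy of the ICF will be kept by the participant, one will be kept by the Investigator". The one group given a different consent procedure is the survey sample: "For the Phase 2: e-survey, return of the questionnaire will imply consent".

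Service users have their own text under Phase 2, Service Delivery, part C (Collecting data from service-users at the time of accessing the service). It confirms that they get both documents: "Clients will be provided with a Participant Information Sheet and Participant Consent Form". Of the information sheet it says: "They will be invited to take this away if they choose". On follow-up it says "We did not feel that contacting participants after the service to collect follow up data would be appropriate", and the reason given is "risk of breach of confidentiality / potential to raise suspicions with abusive partners".

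Three other general provisions bear on later contact. Data Protection and Patient Confidentiality keeps personal data for 12 months after the study "so that the Chief Investigator may provide participants with a summary of the research", if they want one. Engagement and Dissemination gives participants the option of project updates. The Consent section requires a newly signed form after an amendment that might affect participation. None of the three mentions service users.

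**The concern.** For clients the protocol treats discovery by a partner as serious enough to forgo follow-up data. The background section on timing of access describes people experiencing abuse as often under a partner's control. The PPIE findings report that pharmacies were liked partly because a visit can be explained away. A signed and dated form for a domestic abuse and suicidal ideation study, kept by the client, works against that discretion. The risk comes from a research procedure and not from the service.

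Harm of this kind would be hard for the study to see. All client data are collected in the consultation. Progression criterion 15 (client experience) draws on monthly visits, mentoring and staff focus groups, all of which report through staff. A form found at home would come to light mainly if the client returned and said so.

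**Working it through.** No arithmetic applies; the check sets the provisions side by side.

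1. **Does the copy rule reach service users?** Yes. The Consent section covers all participants and gives a different procedure only to the e-survey. Part C confirms that clients are given a consent form, and that consent is taken for Part A and Part B as appropriate. A client who agrees to Part A only is therefore also within the rule.

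2. **Does the client text override it?** Not for the consent form. The choice about taking a document away follows directly on the sentence about going through the information sheet, and that sheet is what it refers to.

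3. **How do the two documents compare?**

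| Document | Signed and dated by the client | Rule for the client |
|---|---|---|
| Information sheet | No signature stated | Taken away if the client chooses |
| Consent form | Yes | A copy kept by the participant, no choice stated |

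The optional rule covers the unsigned document and the unconditional rule covers the one bearing the client's signature.

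4. **Does another section deal with it?** Adverse Events says the delivery protocol will take account of discretion and confidentiality until the client has left the pharmacy. It does not mention the consent form or what happens to it afterwards.

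5. **Do the general provisions on later contact exclude clients?** No. The summary, the updates and re-consent are all worded for participants at large, with no exclusion and no safe-contact arrangement. The summary and updates are at the participant's wish. Re-consent is not, although a client whose data all come from the consultation would seldom meet its trigger.

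**The case against.** The consent section is general text. It speaks of a researcher or recruiting investigator, whereas pharmacy staff take clients' consent, and it says a copy is kept, not that paper must be carried home. The choice about the information sheet shows that the authors had thought about take-home paper for this group. The procedures had PPIE input and were to be refined in Phase 1. Staff are told to invite clients at Levels 1 and 2, and Level 3 is handled separately. The client consent form is not in the text available, so it cannot be checked whether it carries the full title or a discreet service name. Finally, a participant's copy protects the participant.

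Much of this is fair, but it does not remove the fault. The general rule is the only one stated for the form, and staff following the protocol would apply it. The draft triage grid places people wanting to escape, and people with physical or sexual harm, at Level 2, so restricting invitations to Levels 1 and 2 does not exclude clients at risk from a partner. A discreet title would reduce the exposure, but a signed form would remain. The protective value of a copy is a reason to keep the offer, not to leave the client without a choice.

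A reader might go further and infer that the protocol forbids all later contact with clients, and that the study summary breaches this. The documents do not support that. What part C rejects is contact to collect follow-up data; a summary sent at the participant's request is a different act.

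**Conclusion.** The point holds in a limited form. As written, a consenting domestic abuse client keeps a signed study consent form, and the client-specific text, which names a partner's suspicion as a risk, makes no provision for that. This rests on reading the copy rule literally and on the consent section applying to clients, which part C confirms. The partner rationale concerns domestic abuse clients and need not apply to every client with suicidal ideation.

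The provisions on summaries, updates and re-consent are a secondary matter of reconciliation. A reader might infer that clients would in fact be contacted. The documents do not show this: no contact details are listed among the data collected in the consultation, and the wording serves every participant group. The defect is only that service users are not excluded.

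No figure can be put on the risk. The Study Summary makes the number of service users an outcome of the trial, and no discovery rate is given. It is also possible that some clients would decline consent rather than hold the form, but the documents offer nothing to judge that by. No statistical quantity in the plan changes.

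**What to change.** In the Consent section, add a rule for service users: the client is offered a copy of the consent form and may take it, receive it in another form of their choosing, or leave it held by the study. Record the choice. Cross-refer to this rule from part C, so that the information sheet and the consent form are handled alike.

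In Data Protection, Engagement and Dissemination, and the re-consent sentence of the Consent section, state how each provision applies to service users. If no contact details are held for them, say so, and say that summaries and updates reach them through the study website only.

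The cost is a wording amendment, one extra item on the consultation record and ethics committee agreement. The drawback is that some clients will not hold their own copy. The right to one is kept.
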